3.7. Multiple Comparisons/Multiplicity

No adjustments for multiplicity will be conducted for this trial.

3.8. Subpopulations

No analyses of participant subgroups are planned.

3.9. Withdrawals, Dropouts, Loss to Follow-up

Participants who are withdrawn or discontinued from the study will not be replaced.

3.10. Missing, Unused, and Spurious Data

In general, other than for AE and concomitant treatments, missing data will not be imputed or replaced, and calculations will be done on reported values.

When summarizing adverse event data, partial dates will be handled as follows. If any of the day, month, or year is missing, the onset date will be set to the earliest date that is consistent with any non-missing date information, unless the non-missing date information is the same as study treatment start. In this case, to conservatively report the event as treatment-emergent, the

onset date will be assumed to be the date of start of treatment. A completely missing onset date will be coded as the day of start of treatment. If the resulting imputed start date is later than a reported stop date, the start date will be imputed as the stop date. Date imputation is used only to determine treatment emergence; in by-patient listings, partial dates will be presented as recorded.

A prior medication is defined as any medication that has a stop date before the start of the trial (prior to Dose #1 on Day 0). A concomitant medication is defined as any medication that has a stop date that is on or after the date of first dose of study drug. For prior and concomitant medications, partial start dates will not be imputed, as stop dates determine prior versus concomitant. Partial stop dates will be assumed to be the latest possible date consistent with the partial date.

Partial stop dates of prior and concomitant medications will be assumed to be the latest possible date consistent with the partial date. Data for all prior and concomitant medications will be summarized with percentages for participants in the safety and mITT populations.

3.11. Visit Windows

It is expected that all visits should occur according to the protocol schedule. All data will be tabulated per the evaluation visit as recorded on the clinical report form (CRF) even if the assessment is outside of the visit window. In data listings, the relative day of all dates will be presented.

3.12. Interim Analyses

No formal interim analyses are planned for this study. However, safety and tolerability will be assessed by the DSMB for the participants in each study group.

A Sponsor unblinded review of the Week 10 immunogenicity and safety data will be made during Part 1, when all evaluable data observations are available for determination of the optimal dose for Part 2.

Additionally, upon completion of the Week 12 visit and availability of immunological data, group-level (INO-4700 or placebo) unblinded summaries of immunogenicity and safety will be produced.

4. STUDY ANALYSES

4.1. Participant Disposition

Participant disposition will be tabulated by study group (A-I) for Part 1 and by treatment group for Part 2, and will include the number screened, the number of screen failures, the number randomized, the number in each population for analysis, the number treated by the highest number of doses received, the number that completed all study treatments and follow-up visits, the number who discontinued prior to completing the study treatment, the number who withdrew prior to completing all follow-up visits, and reason(s) for withdrawal.

A by-participant data listing of study completion information including the reason for premature study withdrawal, if applicable, will be presented.

4.2. Demographics and Baseline Characteristics

Demographics and baseline characteristics will be summarized and presented by study group for Part 1 and treatment group for Part 2. Age, height, weight, and body mass index (BMI) will be summarized using descriptive statistics (number of participants, mean, SD, median, minimum, and maximum). The number and percentage of participants in each sex, race, and ethnicity category also will be presented. These analyses will be conducted on the mITT and PP populations.

No formal statistical comparisons between groups will be performed for demographics, baseline data, or medical history data. Data for each participant will also be provided in data listings.

4.3. Immunology, Safety, and Exploratory Evaluations

4.3.1. Immunology Evaluations

The following immunogenicity analyses will be conducted on participants in the PP and mITT study populations.

In Part 1, the difference in percentage of overall immune responders including seroconverters (i.e. positive titer) between all pairs of INO-4700 study groups will be calculated along with corresponding exact (Clopper-Pearson) 95% CIs. The T and B cell immune responses to INO-4700 will be measured using assays that include ELISA, neutralization, assessment of immunological gene expression, assessment of immunological protein expression, flow cytometry, and ELISPOT.

In Part 2, the primary hypothesis of $H_0: p \leq 70\%$ versus $H_1: p > 70\%$ will be tested with an exact test of a binomial proportion. In addition, the binding antibody titer difference between INO-4700 and placebo will be analyzed using the geometric mean fold ratio and associated 95% confidence interval. Percent neutralizing antibodies and antigen specific cellular immune response differences between INO-4700 and placebo will be analyzed using the difference in medians and associated 95% CIs.

For both Part 1 and Part 2, antigen specific binding antibody titers, MERS-CoV neutralizing antibody titers, antibodies to other coronaviruses, and specific cellular immune responses will

be analyzed by study group and treatment group, respectively. Time to peak post-baseline titers will be summarized using descriptive statistics. Binding antibody titer will be analyzed for each study group using the geometric mean and associated 95% CIs. Percent neutralizing antibodies and antigen specific cellular immune response increases will be analyzed for each study group using medians, inter-quartile range and 95% CIs. Percentage with overall immune response, inclusive of seroconversion and corresponding 95% Clopper-Pearson CIs will be analyzed within each study and treatment group.

All immunologic data will be presented in data listings.

4.3.2. Safety Analyses

All safety analyses will be conducted using the Safety Population. For analyses on Part 1, tabulations will be provided by study group. For analyses on Part 2, tabulations will be provided by treatment group.

Incidences of medical history events will be presented by MedDRA SOC and PT v. 22.1 or higher using the Safety Population.

4.3.2.1. Study Drug Exposure

Study drug information for each participant will be presented in a data listing and will include the date and time of administration, the study part, treatment group, dose, and the location of the injection site. Number of applications of the electroporation and the CELLECTRA™ used will also be presented in the same listing.

4.3.2.2. Adverse Events

All AEs will be coded using the MedDRA SOC and PT coding system (v. 23.0) and displayed in tables by study and treatment groups and by subject in data listings.

Analyses of AEs will be performed for those events that are considered treatment-emergent, where treatment-emergent adverse events (TEAEs) are defined per protocol as any adverse event with onset after the administration of study medication through the end of the study (Week 68), or any event that was present at baseline but worsened in intensity or was subsequently considered drug-related (definite, probable, or possible relationship) by the Investigator through the end of the study.

Laboratory AEs will be assessed and graded in accordance with the “Toxicity Grading Scale for Healthy Adult and Adolescent Volunteers Enrolled in Preventive Vaccine Clinical Trials”, issued in September 2007 (see Protocol [Appendix A](#)).

Adverse events will be summarized by participant incidence rates; therefore, in any tabulation, a participant contributes only once (i.e., the most related occurrence or the most intense occurrence) to each of the incidence rates in the descriptive analysis, regardless of the number of episodes.

All TEAEs will be summarized by frequency, percentage, and, in Part 2, by the difference in the percentage between those who received INO-4700 and their corresponding regimen placebo.

Related SAEs and related Grade 3 or higher AEs will also be analyzed as described above within and between associated placebo in Part 1. The frequencies will also be presented separately by dose number and will be depicted by SOC and PT. Additional frequencies will be presented with respect to maximum severity and relationship to IP. Multiple occurrences of the same AE in a single participant will be counted only once following a worst-case approach with respect to severity and relationship to INO-4700. All serious TEAEs will also be summarized as above.

No formal hypothesis-testing analysis of adverse event incidence rates will be performed.

By-participant listings will be provided for all AEs, participant deaths, SAEs, and AEs leading to withdrawal.

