3.2 PRIMARY ENDPOINTS

Safety Endpoints:

- Incidence of adverse events by system organ class (SOC), preferred term (PT), severity and relationship to investigational product
- Administration (i.e., injection) site reactions (described by frequency and severity)
- Incidence of adverse events of special interest

Immunogenicity Endpoints:

- Overall Immune response
 - MERS-CoV antigen specific antibodies
 - Antigen-specific cytokine-producing T cell responses

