5.0 CLINICAL TRIAL TREATMENT

5.1 INVESTIGATIONAL PRODUCTS (IPs) AND STUDY DEVICE

5.1.1 INO-4700 AND SSC-0001

Investigational product is defined as a pharmaceutical form of an active ingredient or placebo being tested or used as a reference in the study, whether blinded or unblinded.

INO-4700 is the active investigational product to be used in this study. The INO-4700 drug product contains 10 mg/mL pGX9101 in 1X SSC buffer (150 mM sodium chloride and 15 mM sodium citrate). A volume of 0.4 mL will be filled into 2-mL glass vials that are fitted with rubber stoppers and sealed aluminum caps. INO-4700 must be placed in 2–8°C storage immediately upon arrival and requires preparation prior to administration, which is outlined in the pharmacy manual.

pGX9101 is a DNA plasmid expressing a synthetic consensus (SynCon®) Middle East Respiratory Syndrome Human Coronavirus Spike protein (MERS-CoV Spike), driven by a human CMV promoter (hCMV promoter), and with the bovine growth hormone 3' end poly-adenylation signal (bGH polyA). The pGX0001 backbone includes the kanamycin resistance gene (KanR) and plasmid origin of replication (pUC ori).

Sterile saline sodium citrate (SSC) buffer (SSC-0001), which contains sterile 150 mM sodium chloride and 15 mM sodium citrate in 2-mL or 10-mL glass vials, stoppered, and sealed with aluminum caps, will be used as the placebo at the clinical site.

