5.6 USE OF STUDY DEVICE

The CELLECTRA™ 2000 is an investigational device. The instructions for use of the CELLECTRA™ 2000 device are provided in the User Manual. Each clinical site will receive training for use of the CELLECTRA™ 2000 device prior to first dose.

The EP procedure must be performed by qualified personnel. Any individual designated to perform the procedure should be permitted by the relevant local authorities to administer parenteral injections to patients (e.g., MD, DO, RN) in addition to successfully completing device training from Sponsor personnel.

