7.10.4 CAUSAL RELATIONSHIP OF CLINICAL MATERIAL TO ADVERSE EVENTS (AEs)

A causally related AE is one judged to have a possible, probable or definite relationship to the administration of the IP and/or the study device. An AE may also be assessed as not related to the IP and/or the study device. Because the PI is knowledgeable about the subject (e.g., medical history, concomitant medications), administers the IP, and monitors the subject's response to the IP, the PI is responsible for reporting AEs and judging the relationship between the administration of the IP and EP and a subsequent AE. The PI is aware of the subject's clinical state and may have observed the event, and thus may be sensitive to distinctions between events due to the underlying disease process versus events that may be product-related.

Principal Investigators (PIs) should use their knowledge of the clinical trial subject, the circumstances surrounding the event, and an evaluation of any potential alternative causes to determine whether an AE is considered to be related to the IP and/or the study device and the causal relationship reported as "Yes" or "No" accordingly. Causality should be assessed by the PI as related to drug, related to device, or related to both drug and device (i.e., related to both or indiscernible) by the following criteria:

- Yes – there is a reasonable possibility that administration of the clinical trial treatment (drug or device or both drug and device) contributed to the event
- No – there is no reasonable possibility that administration of the clinical trial treatment contributed to the event and there are more likely causes

The following guidance should also be taken into consideration:

- Temporal relationship of event to administration of IP and/or EP

- Course of the event, considering especially the effects of dose reduction, discontinuation of IP, or reintroduction of IP (where applicable)
- Known association of the event with the IP, EP or with similar treatments
- Known association of the event with the disease under trial
- Presence of risk factors in the clinical trial participant or use of concomitant medications known to increase the occurrence of the event

The rationale for the PI's causal assessment is to be recorded on the SAE Report Form.

The Sponsor will assess the overall safety of the IP delivered by EP and determine whether to report expeditiously to the regulatory authority(ies).

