8.5 DESCRIPTION OF STATISTICAL METHODS

8.5.1 PRIMARY SAFETY ANALYSES

The primary analyses for this trial are safety analyses of treatment emergent adverse events (TEAEs), administration site reactions and clinically significant changes in safety laboratory parameters from baseline.

TEAEs are defined for this trial as any AEs/AESIs/SAEs that occur on or after Day 0 following IP administration. All TEAEs will be summarized by frequency, percentage and associated 95% Clopper-Pearson confidence interval, and in Part 2, the difference in the percentage between those who received INO-4700 and their corresponding same regimen placebo together with associated 95% confidence interval. Related SAEs and related Grade 3 or higher AEs will also be analyzed as described above within and between associated placebo in part 1. The frequencies will also be presented separately by dose number and will be depicted by system order class and preferred term. Additional frequencies will be presented with respect to maximum severity and relationship to IP. Multiple occurrences of the same AE in a single subject will be counted only once following a worst-case approach with respect to severity and relationship to IP. All serious TEAEs will also be summarized as above. AE duration will be calculated as AE stop date – AE start date + 1 day. AEs and SAEs that are not TEAEs or serious TEAEs will be presented in listings.

All of these primary safety analyses will be conducted on the participants in the safety population.

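### The relatedness tables use relationship to IP, which excludes the electroporation device, although the protocol's own definition of a related AE includes it

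*SAP*

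**What the plan says.** **What is collected.** Protocol 7.10.4 describes a causally related AE as one with a "possible, probable or definite relationship to the administration of the IP and/or the study device". It then sets the attribution: "Causality should be assessed by the PI as related to drug, related to device, or related to both drug and device", where the last category also covers cases that cannot be told apart. The same section records the relationship as yes or no, and yes includes a contribution from the device alone.

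**What IP means.** Protocol 5.1.1: "Investigational product is defined as a pharmaceutical form of an active ingredient or placebo being tested or used as a reference in the study". The electroporator is dealt with separately in Protocol 5.6: "The CELLECTRA™ 2000 is an investigational device".

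**What is analysed.** The first primary safety endpoint in Protocol 3.2 classifies AEs by "severity and relationship to investigational product", and SAP 1.2.5.1 follows it. For the tables, Protocol 8.5.1 states: "Additional frequencies will be presented with respect to maximum severity and relationship to IP". SAP 4.3.2.2 repeats that sentence. For repeat occurrences of one AE in one participant, Protocol 8.5.1 applies a worst-case rule on relationship to IP. SAP 4.3.2.2 applies it "following a worst-case approach with respect to severity and relationship to INO-4700". The SAP's TEAE definition also admits events already present at baseline that the investigator later judges drug-related.

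**What is not said.** Neither document specifies a table by relationship to the device. Neither says how drug, device and both map to the related category in the tables.

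**The concern.** Every administration in this trial, active or placebo, is an injection followed by electroporation, and the first primary objective is the tolerability of INO-4700 given that way. The protocol therefore collects causality for the combined procedure. The analysis text then takes only the pharmaceutical part of it. If a programmer follows the text as written, a reaction that the investigator calls related, but attributes to the device, is tabulated as not related.

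What is at stake is the stated rate of related events for a drug-device product. Part 1 groups D, E, H and I have two injection-plus-electroporation administrations per dosing visit, and A, B, C, F and G have one. If device-only attributions occur, they could be more frequent in the two-administration groups, and the relationship table is where that would go unseen.

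The change from IP to INO-4700 in the SAP counting rule is a second, smaller problem. IP includes placebo, so the protocol's rule works in every group. INO-4700 is not given to placebo recipients, so the SAP's rule has no clear meaning for them.

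**Working it through.** No calculation applies: no figure in either document depends on this definition. The check is to follow each attribution category from Protocol 7.10.4 through each planned output, using the literal wording.

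| Output | Relatedness term used | Drug only | Device only | Both or indiscernible |
|---|---|---|---|---|
| Investigator's judgement (Protocol 7.10.4) | IP and/or device | related | related | related |
| Primary endpoint (Protocol 3.2, SAP 1.2.5.1) | IP | related | not related | related |
| Relationship frequencies (Protocol 8.5.1, SAP 4.3.2.2) | IP | related | not related | related |
| Related SAEs and related events of Grade 3 and above (Protocol 8.5.1, SAP 4.3.2.2) | none given | related | undetermined | related |
| SAP TEAE clause for events present at baseline | drug | qualifies | does not qualify by this clause | qualifies |
| All TEAEs, AE listings | none needed | counted | counted | counted |
| Administration site reactions, if local | none needed | counted | counted | counted |

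Four things follow.

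1. The first three rows conflict. Under 7.10.4 a device-only event is causally related. Under the endpoint and relationship-table wording, with IP as defined in 5.1.1, it is not.
2. In the fourth row the text does not settle the matter. The broader meaning in 7.10.4 could be carried over. However, the SAP does not restate that meaning, and its explicit relatedness terms are IP, INO-4700 or drug.
3. The TEAE clause has little effect. It concerns only events already present at baseline. Any event with onset after dosing is treatment-emergent whatever its attribution.
4. The last two rows limit the loss. Device-only events leave the related counts, not the safety evaluation.

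On size, let R be the proportion of participants with any event related to drug or device, and d the share of those whose related events are all device-only. The literal table shows R × (1 − d), so the shortfall is R × d. The documents give neither R on this definition nor d, so no value can be put in.

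On the counting rule, SAP section 5 lists two changes: adding the PP population for demographics and concomitant medication, and making PP the key population for immunogenicity. The move from IP to INO-4700 is not among them.

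**The case against.** The best defence is that IP is shorthand. Protocol 7.10.4 already yields a yes/no answer in which a device-only event is yes, and a programmer may simply use that answer. Protocol 7.8 speaks of causal relationship to trial treatment, and Protocol 6.4.5 describes the IP administration procedure as including the electroporation pulses. No CRF or table shell is available to show that the narrow reading would be programmed. This stands as a reason to doubt that events would in fact be lost. It does not remove the conflict in the text: 7.10.4 repeatedly names IP and device as two things, and inclusive wording was available but not used in the endpoint or the tables.

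It is also fair that one- and two-administration regimens can be compared on outputs without a relatedness filter: all TEAEs and administration site reactions. SAP 4.3.2.2.1 adds monitoring of anxiety and pain from the procedure. Device-only attribution may also be rare, since electroporation immediately follows injection at the same site and the investigator may choose the combined category. Both points stand.

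A reader might infer from "following a worst-case approach with respect to severity and relationship to INO-4700" that every related event on placebo would be tabulated as unrelated, emptying that column and distorting the active-placebo contrast. The documents do not support this. The phrase sits only in the rule for repeat occurrences. The sentence before it sets the table by relationship to IP, which includes placebo. All groups receive electroporation, so any effect of the IP wording on the difference between arms is indirect.

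**Conclusion.** The point holds as a conflict between a stated analysis rule and the protocol's own definition of a related AE. On the literal text, device-only events are not related in the primary relatedness endpoint and the relationship tables, and nothing planned shows them by device relationship. This rests on reading IP as Protocol 5.1.1 defines it.

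For related SAEs and related events of Grade 3 and above, the finding is ambiguity. A reader might conclude that device-only events are certainly excluded there as well, but the unqualified term does not show that. Nor do the documents show that device-attributed reactions are what separates the regimens on tolerability.

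The size is unknown and may be small. The clearest effect would be understated related-event rates within each group. The administrative memo that ended the trial before Part 2 leaves the Part 1 tables by group subject to this wording. The AE analyses are descriptive, so no test result depends on it. It should be corrected because it affects a primary safety endpoint and the data needed are already required by the protocol.

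**What to change.** - In Protocol 3.2 and 8.5.1 and SAP 1.2.5.1 and 4.3.2.2, define related, for every relatedness table, as related to IP and/or the study device, consistent with Protocol 7.10.4. State that this covers the analyses of related SAEs and related events of Grade 3 and above.
- In SAP 4.3.2.2, replace INO-4700 in the repeat-occurrence rule, and the drug-related wording in the TEAE clause, with that definition.
- Show related events split into drug only, device only, and both or indiscernible. State in which column a participant falls whose occurrences of the same term carry different attributions.
- Record these changes in SAP section 5.

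The cost is SAP and table-shell wording and slightly more table work, with no new data collection. The downside is that the reported related-event rate may be somewhat higher.
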